10.3.3 Recording and Follow-up of AE and SAE

AE and SAE Recording

- When an AE/SAE occurs, it is the responsibility of the Investigator to review all documentation (e.g., hospital progress notes, laboratory and diagnostics reports) related to the event.
- The Investigator will then record all relevant AE/SAE information in the eCRF.
- It is **not** acceptable for the Investigator to send photocopies of the patient's medical records to the Sponsor in lieu of completion of the AE/SAE eCRF page.
- There may be instances when copies of medical records for certain cases are requested by the Sponsor. In this case, all patient identifiers, with the exception of the patient number, will be redacted on the copies of the medical records before submission to the Sponsor.
- The Investigator will attempt to establish a diagnosis of the event based on signs, symptoms and/or other clinical information. In such cases, the diagnosis (not the individual signs/symptoms) will be documented as the AE/SAE.

Assessment of Intensity

The Investigator will make an assessment of severity for each AE and SAE reported during the study and classify it into one of Grade 1 through 5 using the NCI-CTCAE v5.0:

- Grade 1: Mild; asymptomatic or mild symptoms; clinical or diagnostic observations only; intervention not indicated.
- Grade 2: Moderate; minimal, local or noninvasive intervention indicated; limiting ageappropriate instrumental activities of daily living (ADL)*.
- Grade 3: Severe or medically significant but not immediately life-threatening; hospitalization or prolongation of hospitalization indicated; disabling; limiting self-care ADL**.
- Grade 4: Life-threatening consequences; urgent intervention indicated.
- Grade 5: Death related to AE.

*Instrumental ADL refer to preparing meals, shopping for groceries or clothes, using the telephone, managing money, etc.

**Self-care ADL refer to bathing, dressing and undressing, feeding self, using the toilet, taking medications and not bedridden.

An event is defined as 'serious' when it meets at least one of the predefined outcomes as described in the definition of an SAE, NOT when it is rated as Grade 3 or higher.

Assessment of Causality

- The Investigator is obligated to assess the relationship between study drug and each occurrence of each AE/SAE.
- A "reasonable possibility" of a relationship conveys that there are facts, evidence and/or arguments to suggest a causal relationship, rather than a relationship cannot be ruled out.
- The Investigator will use clinical judgement to determine the relationship.
- Alternative causes, such as underlying disease(s), concomitant therapy and other risk factors, as well as the temporal relationship of the event to study drug administration will be considered and investigated.
- The Investigator will also consult the IB and/or Product Information, for marketed products, in his/her assessment.
- For each AE/SAE, the Investigator must document in the medical notes that he/she has reviewed the AE/SAE and has provided an assessment of causality.
- There may be situations in which an SAE has occurred, and the Investigator has minimal information to include in the initial report to the Sponsor. However, it is very important that the Investigator always make an assessment of causality for every event before the initial transmission of the SAE data to the Sponsor.
- The Investigator may change his/her opinion of causality in light of follow-up information and send an SAE follow-up report with the updated causality assessment.
- The causality assessment is one of the criteria used when determining regulatory reporting requirements.

Follow-up of AE and SAE

- The Investigator is obligated to perform or arrange for the conduct of supplemental measurements and/or evaluations as medically indicated or as requested by the Sponsor to elucidate the nature and/or causality of the AE or SAE as fully as possible. This may include additional laboratory tests or investigations, histopathological examinations or consultation with other health care professionals.
- New or updated information will be recorded in the originally completed eCRF.

• The Investigator will submit any updated SAE data to the Sponsor within 24 hours of receipt of the information.

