Circulatory tumor DNA a,d	2×4	Х	Х	Х	Х

^a Plasma

^b Sample should be collected after the patient has completed 7 days of NOX66 treatment in Cycle 2 and prior to dosing on Day 1 of Cycle 3.

^c Baseline samples to be collected only after eligibility confirmation or on Day 1 prior to NOX66 administration.

^d Only at pre-selected sites that have peripheral blood mononuclear cell isolation capabilities in Australia and the United States of America.

Table 1-5Optional Archival Tissue Collection and Fresh Biopsy Sampling
Schedule – Part 1 and Part 2 (All Patients)

Assay	Screening	After Cycle 3 treatment
Archival tissue if available (Optional)	Х	
Fresh biopsy (Optional)		Х

NOTE: Available archival tissue samples will only be requested if a fresh tissue biopsy is collected after Cycle 3. Provision of a fresh biopsy sample and/or an archival tissue sample is optional.

2 Introduction

The term "study drug" throughout the protocol, refers to NOX66. In addition, the terms participant and patient are used interchangeably.

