2.3.3 Overall Benefit: Risk Conclusion

Considering the measures taken to minimize risk to patients participating in this study, the potential risks identified in association with NOX66 are justified by the anticipated benefits that may be afforded to patients with mCRPC and other solid tumors.

3 Objectives and Endpoints

Objectives	Endpoints				
Primary Objectives and Endpoints					
Part 1 (Dose Escalation):	The primary objective for Part 1 will be determined based on the count of DLTs.				
To determine the MTD and RP2D of NOX66 in combination with low-dose EBRT in patients with any	• MTD is defined as the dose level at which no more than 1 patient out of 6 experiences a DLT at the end of Cycle 1.				
solid tumor	• RP2D is the highest dose administered at which no more than 1 patient out of 6 experiences a DLT at the end of Cycle 1 and the dosage form, including the dosing frequency, is acceptable to patients.				

Table 3-1Objectives and Endpoints

Objectives	Endpoints
 Part 2 (Dose Expansion): Arm 1: To evaluate the effect of NOX66 on PSA response in patients with mCRPC. Arm 2: To evaluate the effect of NOX66 on DCR in patients with BC and NSCLC. 	 PSA response is defined as the proportion of patients with a reduction in PSA in plasma (ng/mL) of ≥ 30% from baseline at the end of Cycles 3 and 6. DCR is measured by the percentage of patients with a best overall confirmed response of CR or PR and SD.
Secondary	V Objectives and Endpoints
Characterize the safety and tolerability of NOX66	Safety and tolerability of NOX66 as determined by AEs, TEAEs, clinical laboratory evaluations, vital signs, 12-lead ECG and physical examinations.
Evaluate the safety and tolerability of both doses of EBRT	Safety and tolerability of both doses of EBRT as determined by AEs, TEAEs, clinical laboratory evaluations, vital signs, 12-lead ECG and physical examinations.
Evaluate the exposure of idronoxil	Concentration of idronoxil and selected metabolites in plasma and derived PK parameters, including but not limited to: C _{max} , T _{max} , AUC _(0-t) , AUC ₍₀₋₆₎ , AUC ₍₀₋₁₂₎ , AUC _(0-inf) , C _{min} and t ₂ , as data permit.

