Patients in both study parts will be followed up by phone for AEs/SAEs for 30 days after the last dose of study drug or until resolution or stabilization of ongoing AEs/SAEs deemed at least possibly related to the study drug, whichever is longer. All patients (including patients who discontinued the study early for reasons other than disease progression) will be followed up approximately every 12 weeks (\pm 2 weeks) after completion of the treatment period for disease progression up to 12 months, and for safety until death, or the patient is lost to follow-up. Patients who discontinued the study early for reasons other than disease progression will attend the clinical unit for the follow-up visits. Patients will receive the study drug until disease progression, unacceptable toxicity, withdrawal of consent, initiation of new anticancer therapy, withdrawal of the patient by the Investigator or termination of the study by the Sponsor. Tumor imaging and disease response assessments will be performed for up to 12 months after the last dose of study drug until disease progression, withdrawal of consent, initiation of new anticancer therapy, the patient is lost to follow-up or death, whichever comes first.

The study will include 4 dose cohorts (Part 1) and 2 treatment arms (Part 2):

- Part 1: Eligible patients with any solid tumor will be enrolled in one of 4 dose cohorts:
 - Dose Cohort 1: 800 mg NOX66 (Days 1 to 14 [Cycle 1]) + EBRT (Days 2 to 11 of Cycle 1, depending on the number of fractions to be administered). From Cycle 2 onwards, 800 mg NOX66 will be administered on Days 1 to 7.
 - Dose Cohort 2: 1200 mg NOX66 (Days 1 to 14 [Cycle 1]) + EBRT (Days 2 to 11 of Cycle 1, depending on number of fractions to be administered). From Cycle 2 onwards, 1200 mg NOX66 will be administered on Days 1 to 7.
 - Dose Cohort 3: 1600 mg NOX66 (Days 1 to 14 [Cycle 1]) + EBRT (Days 2 to 11 of Cycle 1, depending on number of fractions to be administered). From Cycle 2 onwards, 1600 mg NOX66 will be administered on Days 1 to 7.
 - Dose Cohort 4: 2400 mg NOX66 (Days 1 to 14 [Cycle 1]) + EBRT (Days 2 to 11 of Cycle 1, depending on number of fractions to be administered). From Cycle 2 onwards, 2400 mg NOX66 will be administered on Days 1 to 7.
- Part 2: Eligible patients will be enrolled in 1 of 2 treatment arms:

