7.1.2.2 Assessment of Dose-limiting Toxicities

A DLT is defined as an AE that occurs during Cycle 1 (Day 1 to Day 21) that is assessed as unrelated to the disease, intercurrent illness or concomitant medications and that, despite optimal therapeutic interventions, meets any of the following criteria (judged to be associated with NOX66 alone or in combination with EBRT [possibly, probably or definitely related to]):

- 1. Grade 3 or higher non-hematological toxicities (excluding alopecia) with the following exceptions:
 - a. Grade 3 nausea/vomiting or diarrhea < 72 hours with adequate antiemetic and other supportive care

- b. Grade 3 fatigue < 1 week
- c. Grade 3 or higher electrolyte abnormality that lasts 24 to 72 hours, is not clinically complicated, and resolves spontaneously or responds to conventional medical drugs
- 2. Grade 4 non-hematologic (non-laboratory) toxicity of any duration.
- 3. Grade 3 or Grade 4 febrile neutropenia of any duration.
- 4. Grade 4 neutropenia or thrombocytopenia > 5 days.
- 5. Grade 3 thrombocytopenia with bleeding.
- 6. Grade 3 thrombocytopenia in combination with a Grade 3 or greater blood and lymphatic system disorder.
- 7. Grade 3 AST or ALT that is associated with a Grade 2 or greater rise in bilirubin that lasted for more than 7 days.
- 8. Any AST or ALT > $8 \times$ ULN regardless of duration (5 to $8 \times$ ULN for up to 2 weeks is allowed).
- 9. Any AE that results in a treatment delay or hold of > 14 days.

Grading of DLTs will follow the guidelines provided by the National Cancer Institute-Common Terminology Criteria for Adverse Events (NCI-CTCAE) v5.0.

All AEs of the grades specified above count as DLTs unless they are clearly and incontrovertibly due to disease progression or extraneous causes.

After all patients enrolled in a cohort complete Cycle 1, and the data from these patients are available, a dose escalation meeting will be conducted. At least 3 evaluable patients are required in order to proceed with DLT evaluation for each cohort.

The criteria for determination of an evaluable patient for a dose escalation decision or determination of the MTD, must include:

- Patient who experienced a DLT during the 21-day treatment cycle (Cycle 1), or
- Patient who has not experienced a DLT and has taken at least 80% of the prescribed daily doses of NOX66 and completed all safety evaluations.

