9.4.7 Secondary Endpoint(s)

9.4.7.1 Safety of NOX66 and Both Doses of EBRT

Safety profiles will be summarized by NOX66 dose cohort and separately by EBRT dose cohort (Part 1) or treatment arm and separately by EBRT dose cohort (Part 2) and will be based on the Safety Analysis Set.

Adverse events will be coded using the MedDRA v22.0 or higher and will be graded according to the NCI-CTCAE v5.0. Treatment-emergent AEs are defined as those AEs that either start or

worsen in severity on or after the date of first administration of study drug and on or before 30 days after the last dose of study drug.

Treatment-emergent AEs will be summarized by severity grade and relationship to study drug. Serious AEs, serious TEAEs and TEAEs leading to discontinuation of study drug or to death will be presented.

Changes in clinical laboratory values, vital signs, ECGs and physical examinations will be summarized over time.

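### EBRT safety is a secondary objective, but AE causality, the relatedness tables and the TEAE window are tied to NOX66 alone, so EBRT-attributed events cannot be tabulated as planned

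*Combined protocol and SAP*

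**What the plan says.** Table 3-1 (Section 3) lists as a secondary objective: "Evaluate the safety and tolerability of both doses of EBRT". The endpoint is AEs, TEAEs, laboratory values, vital signs, ECGs and physical examinations.

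The opening of Section 2 states that the term study drug "throughout the protocol, refers to NOX66". Section 6 has a more general definition, but Table 6-1 lists only NOX66 and the Section 6 text names EBRT separately from study drug.

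That term then governs the safety reporting:

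- Section 10.3.3, investigator causality: "The Investigator is obligated to assess the relationship between study drug and each occurrence of each AE/SAE".
- Section 10.3.4, sponsor review of SAEs: causality is judged against study drug.
- Section 9.4.7.1, tables: "Treatment-emergent AEs will be summarized by severity grade and relationship to study drug". The TEAE window in the same section runs from the first study drug dose to 30 days after the last.
- Section 4.1, extended follow-up: beyond 30 days, AEs are followed "until resolution or stabilization of ongoing AEs/SAEs deemed at least possibly related to the study drug, whichever is longer". The synopsis and footnote t of the Schedule of Activities say the same.

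EBRT appears in three other places that matter here. Section 9.4.7.1 plans that "Safety profiles will be summarized by NOX66 dose cohort and separately by EBRT dose cohort". Section 7.1.2.2 counts as DLTs events "judged to be associated with NOX66 alone or in combination with EBRT". Appendix 10 (Section 10.10) requires interruption of fractionated treatment for Grade 3 or higher reactions caused by radiation.

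**The concern.** The protocol asks about EBRT safety and relies on judgements about radiation causality in two of its rules, but nothing in it requires those judgements to be recorded for an adverse event. NOX66 is being studied as a radiosensitizer, so reactions in the irradiated field are of particular interest. One attributed to radiation alone would be classed as not related to study drug, alongside progression and intercurrent illness. Attribution not captured at the time is hard to rebuild later.

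The summary by EBRT dose does not replace attribution. Every patient also takes NOX66, the EBRT dose is the investigator's choice, and the period summarized depends on NOX66 duration rather than on radiation. Sites may also follow the same unresolved radiation reaction differently, because the follow-up rules disagree.

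**Working it through.** The plan gives no figure for this point. The check is a reading of the text plus day counts.

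**Attribution.** Section 10.3.3 lists "Alternative causes, such as underlying disease(s), concomitant therapy and other risk factors" among the things to weigh, but only in deciding whether NOX66 is the cause. The DLT listing in Section 9.4.6.1 likewise shows relationship to study drug. The protocol text requires no relationship to EBRT to be recorded and plans no table of it.

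**Window.** Inputs from Section 4.1: Cycle 1 lasts 21 days with NOX66 on Days 1 to 14; later cycles last 14 days with NOX66 on Days 1 to 7; the first fraction is on Day 2 and the remaining fractions fall by Day 11.

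- Last NOX66 day = 14 for Cycle 1, or 22 + 14(c − 2) + 6 for cycle c ≥ 2.
- Window end = last NOX66 day + 30.
- Cover after EBRT = window end − 11, taking the latest last fraction.

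| Case | Last NOX66 day | Window end | Days after a Day 11 fraction |
|---|---|---|---|
| NOX66 stopped Day 3 (assumed) | 3 | 33 | 22 |
| Cycle 1 dosing completed | 14 | 44 | 33 |
| Cycle 3 dosing completed | 42 | 72 | 61 |
| Cycle 6 dosing completed | 84 | 114 | 103 |
| Cycle 13 dosing completed | 22 + 154 + 6 = 182 | 212 | 201 |

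In the Cycle 13 case, the span from first fraction to 30 days after a Day 11 fraction is Days 2 to 41, or 40 days. That is 40/212 = 19% of the window, assuming no repeat EBRT. Of the other 172 days (81%), all but Day 1 come later.

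Cover falls below 30 days only when the last NOX66 dose precedes the last fraction. Sections 4.1, 6.1.1 and 6.6.1 allow further EBRT courses, and no window is tied to them.

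**Follow-up rules side by side.**

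- Narrow: the synopsis, Section 4.1 and footnote t extend follow-up only for events at least possibly related to study drug. Section 8.3.1 ends AE collection 30 days after the last dose.
- Wider: Section 8.3 makes the investigator responsible for AEs that are serious, that led to discontinuation, or that are related to study drug or to the study. Section 7.2 follows adverse reactions without naming an agent. Section 8.3.3 follows every SAE whatever its cause. The Schedule of Activities marks adverse events at the 12-weekly follow-up.
- Late SAEs: Section 8.3.1 includes those related to study participation. Section 10.3.4 refers only to study drug, and its US text makes that an explicit restriction.

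**The case against.** The other side has real points. The endpoint in Table 3-1 does not itself ask for EBRT attribution, and Section 9.4.7.1 delivers the listed measures by EBRT dose in a study that Section 9.1 declares descriptive. The Safety Steering Committee reviews both EBRT doses (Section 7.1.2.1) and radiotherapy interruptions are counted (Section 8.2.8). A reader might infer that the EBRT objective cannot be answered at all. The documents do not support that: it is partly answered, without causal attribution or a relevant window.

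A reader might also infer that unresolved EBRT reactions are simply dropped at 30 days. That too goes beyond the text. SAEs are followed regardless of cause, and Sections 7.2 and 8.3 can be read to cover radiation reactions because the study itself mandates EBRT. The fault is conflict between rules, not absence of follow-up.

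Nor do the relatedness tables lose all in-field toxicity. An event thought to be enhanced by NOX66 is possibly related to NOX66 and enters them, and in Part 1 it can count as a DLT. Only events attributed purely to EBRT are classed as unrelated, and these still appear among all TEAEs.

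The long window is over-inclusive rather than a loss of data. EBRT dates are listed (Section 9.4.5), so an EBRT-anchored display could be built at analysis from the AEs collected. The short window needs an unusual patient; anyone completing Cycle 1 dosing has at least 33 days.

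Finally, the eCRF is not in the documents and Section 9.4 defers further detail to a SAP, so the finding is about the protocol text. None of this supplies a recorded relationship to EBRT.

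**Conclusion.** The point holds in this form. As written, AEs attributed to EBRT cannot be tabulated, and the by-EBRT-dose summary covers a period set by NOX66 duration. With EBRT ending on Day 11, cover after the last fraction runs from 22 days in the assumed Day 3 stop to 201 days through Cycle 13. Repeat courses are not anchored.

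The attribution gap applies to any AE judged due to radiation, in both parts. The short window is confined to patients whose last NOX66 dose precedes their last fraction. Exposure to the follow-up conflict is confined to non-serious AEs judged unrelated to NOX66; for late SAEs, the reporting criteria differ between Sections 8.3.1 and 10.3.4.

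The day counts assume dosing on schedule without delays and, for the 19% figure, no repeat EBRT. No sample size or error rate is involved. The change should be made, since it is cheap and the protocol's own objective calls for it.

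**What to change.** 1. In Section 10.3.3 and on the AE eCRF page, record relationship to NOX66 and to EBRT as separate items, allowing either or both.
2. In Section 9.4.7.1 and the synopsis, add TEAE tables by relationship to EBRT. For the EBRT-dose summary, add a display of AEs from the first fraction to 30 days after the last fraction of each course.
3. In the synopsis, Sections 8.3.1 and 9.4.7.1 and footnote t, end the AE collection and TEAE window 30 days after the later of the last NOX66 dose and the last EBRT fraction.
4. Reconcile the follow-up and late-SAE wording in the synopsis, Section 4.1, footnote t and Sections 8.3.1 and 10.3.4 with Sections 7.2, 8.3 and 8.3.3 and the follow-up column of the Schedule of Activities.

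The cost is one eCRF field, a few tables, amendment wording and slightly longer follow-up for a few patients. Attribution will remain investigator judgement in an open-label study where everyone receives both treatments, and the EBRT dose groups will still be unrandomized; the tables should be read with both in mind.

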10.3.4 Reporting of SAE

For studies in the US:

The Investigator must report any SAEs in the eCRF/EDC system within 24 hours of becoming aware of the event. In the event the EDC system is down, the Investigator must complete the SAE form and provide the completed form to the Parexel Clinical Studies Safety Center using the email address provided to the sites on the eCRF/SAE form.

When sending the completed SAE form via email, state that you are reporting an SAE and give the Investigator's name, your name, the telephone number where you can be reached and the protocol number and title. The event must be documented in the eCRF/EDC system when it is back online.

The Investigator and the Sponsor (or Sponsor's designated agent) will review each SAE report and the Sponsor/Parexel will evaluate the seriousness and the causal relationship of the event to study drug. In addition, the Sponsor (or Sponsor's designated agent) will evaluate the expectedness according to the reference document (IB or Summary of Product Characteristics). Based on the Investigator and Sponsor's assessment of the event, a decision will be made concerning the need for further action.

All SAEs will be recorded from signing of informed consent until 30 days after the last dose of study drug. Serious adverse events occurring after the end of the study and coming to the attention of the Investigator must be reported only if they are considered (in the opinion of the Investigator) causally-related to study drug.

SERIOUS ADVERSE EVENT REPORTING INSTRUCTIONS Parexel International Corporation Clinical Studies Safety Center Medical Monitor Drug Safety Specialist (See SAE Reporting Instructions)

- Telephone the Medical Monitor using the number provided to sites to inform him/her that you have completed the SAE eCRF page/SAE form. If the Medical Monitor is not available or you are calling after business hours (8:30 am to 5:30 pm Eastern time, Monday to Friday), leave a message in his/her voice mailbox.
- 2. Provide the Medical Monitor with the Principal Investigator's name, your name, the telephone number where you can be reached and the protocol number and title.
- 3. Inform the Medical Monitor within 24 hours of becoming aware of the event and provide any supporting documentation to him/her within this time frame.
- 4. After business hours, the Medical Monitor may be reached through Parexel's 24-hour answering service on the number provided to the sites. Give the answering service the protocol number, the study drug name and the Sponsoring pharmaceutical company.

For Studies in the EU:

All SAEs that occur during the study and all SAEs occurring up to 30 days after receiving the last dose of study drug, whether considered to be associated with the study drug or not, must be reported within 24 hours in the eCRF/EDC system. If the EDC system is offline for any reason, the Investigator should complete the SAE form and provide the completed form to the Parexel Safety Contact using the email address provided to the sites.

SAEs occurring after the end of the study should be reported to the Sponsor/Parexel by the Investigator if the Investigator considers there is a causal relationship with the study drug.

The minimum information required for an initial report is (in situations where the EDC system is offline at time of reporting):

- Name of person sending the report (e.g., name, address of Investigator).
- Patient identification (Screening/participant number, initials, NOT patient name).
- Protocol number.

- Description of SAE.
- Causality assessment, if possible.

However, as far as possible all points on the SAE form should be covered in the initial report or the completed SAE form itself must be emailed to the Parexel Safety Contact using the information provided to study sites. The original SAE form must then be sent by mail to the Parexel Safety Contact. In addition, the event must be documented in the eCRF/EDC system when it is back online.

In case the Parexel Safety Contact cannot be contacted (e.g., out of normal working hours or at weekends), an automated reporting service is available. The required information should be emailed, and a message should be left on the voicemail service (the relevant phone number/email address will be provided to all sites).

After receipt of the initial report, the safety center will review the information and, if necessary, contact the Investigator, to obtain further information for assessment of the event. Parexel will be responsible for all information processing and reporting according to local legal requirements. Where necessary, Investigators will inform regulatory authorities in their own countries.

For Studies in Australia:

The Investigator must report any SAEs in the eCRF/EDC system within 24 hours of becoming aware of the event. In the event the EDC system is down, the Investigator must complete the SAE form and provide the completed form to the Parexel Clinical Studies Safety Center using the email address provided to the sites on the eCRF/SAE form. The original SAE form must be sent by mail to the Parexel Safety Contact and the event must be documented in the eCRF/EDC system when it is back online.

All SAEs will be recorded from signing of informed consent until 30 days after the last dose of study drug. Serious adverse events occurring after the end of the study should be reported to the Sponsor/Parexel by the Investigator if the Investigator considers there is a causal relationship with the study drug.

The minimum information required for reporting of an SAE is (in situations where the EDC system is offline at the time of reporting):

- Contact details of the person sending the report (e.g., name, address, phone number).
- Patient identifier (e.g., Screening/participant number, initials, date of birth, but not their full name).

- Details of the product involved.
- Protocol number.
- Details of the suspected SAE (including causality and severity assessment).

In case the Parexel Safety Contact cannot be contacted (e.g., out of normal working hours or at weekends), an automated reporting service is available. The required information should be emailed, and a message should be left on the voicemail service (the relevant phone number/email address will be provided to all sites).

After receipt of the initial report, the safety center/Sponsor will review the information and, if necessary, contact the Investigator, to obtain further information for assessment of the event. Based on the Investigator and Sponsor's assessment of the event, a decision will be made concerning the need for further action. Parexel will be responsible for all information processing and reporting according to local legal requirements. Where necessary, Investigators will inform regulatory authorities in their own countries.

